be familiarized with the grid using a haptic model. The spatial imagery task involves presentation of auditory cues to a four- or five-step sequence in the grid, with the constraint that there will be no diagonal cues. Participants are asked to imagine the sequence and mentally compute the shortest path back to the start from the end-point (**Fig. 3**). This is termed path integration and is a test relevant to formation of cognitive maps, which is a key aspect of spatial navigation. Participants will use a joystick to indicate via the direction of the shortest path from the end-point to the start.

Real-world task: A textured 5x5 grid will be laid out on the floor of the CVNR Movement Studies Laboratory (MSL). Each cell of the grid will be a square of 32 inches side (based on an average step length of 32 inches). Subjects will be oriented to the grid by walking around the grid, just inside the perimeter, and also walking across the grid starting in the central cell of an end row, walking directly across to the central cell of the opposite end row, then back to the start, and repeating the process for the orthogonal direction. These orienting steps will be repeated a few times until the subject is comfortable with the layout of the grid and the corresponding cell numbers. Then, audio cues will be presented directing the subject to walk in sequences similar to those in the spatial imagery task. Movable lengths of 2x4's will be used to bound the specific paths to walk, the subject using his/her long white cane in a natural way to detect the 2x4's as the edge of the path being walked. The 2x4's will help the subject walk in straight lines along the path, and insure they turn at the correct points. The MSL is equipped with a WorldViz PPT tracking system that can track motion using up to 32 sensors. Once the sequence is completed, the subject will be instructed to point to the starting location using the cane. Infrared transmitters affixed to the cane for the session will detect and record the pointing angle (to an accuracy of $\pm 4^\circ$ of solid angle), and performance will be measured as the angular error of pointing.

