Interventions: The experimental intervention (spatial cognitive training) will comprise repeated practice of the spatial imagery task with feedback after each trial. Training will be conducted in the participant's home using an iPad issued to the subject at the initial visit, and live video communication with a research assistant at the CVNR over the internet. The iPad will be programmed to allow administration of the spatial imagery task. As in the version of the spatial imagery task administered at initial and final testing, audio cues will trigger mental navigation through the grid using audio cues, with haptic reinforcement via tactile overlays for the screen (to permit sensory facilitation of learning). Following each sequence traced, subjects will be asked whether the shortest path back to the origin intersects with the sequence traced or not. If the answer is incorrect, the research assistant will show the correct path for the subject to trace mentally and haptically. In the control intervention, subjects will be taught letter correspondences to the numbers (e.g. 1->A, 2->B and so on until 25->Y), using a similar setup and procedure as in the experimental intervention.

Behavioral measures: The following behavioral measures will be collected before and again after training with the experimental and control interventions: (1) Performance (directional accuracy and response time [RT]) on the spatial imagery task will be acquired during fMRI scanning. (2) In addition, pointing accuracy will be measured on the real-world path integration task in the MSL, in terms of the angular difference between the target of pointing and the actual initial position. (3) We will also measure performance, with standardized neuropsychological tests, at baseline as well as at post-training, on (a) spatial memory using a haptic version (produced in the [name] lab using textured blocks) of the Corsi block test (Kessels et al., 2000), (b) the verbal memory tests of immediate and delayed memory from the RBANS (Randolph, 1998) and (c) verbal working memory tested by the Forward and Backwards Verbal Digit Span test from the Wechsler Adult Intelligence Scale (Wechsler, 2008). A research assistant will be trained by the PI and [name], Co-investigator on this project, to administer all the tests, as well as the training procedures.

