Imaging measures: The following imaging analyses will be conducted on data acquired before and again after training with the experimental and control interventions: (1) A univariate contrast between the experimental and control conditions will provide insight into the brain regions responsible, and the **magnitudes of activation** in key brain regions will be assessed. (2) Multivariate pattern analyses (Kriegeskorte, 2008) will be used to assess **representational similarity in the neural representations of paths**. (3) Further, we will use **multivariate effective connectivity analyses**, which our group has considerable experience with (Hampstead et al., 2011; [name] et al., 2013; Lacey et al., 2014), to examine patterns of connectivity during task performance. (4) In addition, we will assess **resting-state connectivity** patterns using the activated regions as seeds. (5) Finally, we will also acquire diffusion tensor imaging (DTI) scans to assess **structural connectivity**.

Imaging design: The same spatial imagery task as outlined above will be used during fMRI scanning in an event-related design, with pseudorandomly interleaved trials of a control task requiring judgment of whether the majority of numbers in the audio sequence are odd or not. On each trial, the stimulus presentation will occupy 4s or 5s, depending on whether the sequence comprises 4 or 5 steps in the grid. These two trial durations will be interleaved in pseudorandom order, as will experimental and control trials. Participants will be verbally instructed to make their keypress response following the last auditory cue. A blank interval varying from 4-8s will intervene between trials: this jitter allows for better estimation of the signal on each trial than designs with a fixed inter-trial interval. Each run of trials will also include six pseudorandomly interspersed 10s blank periods for estimation of baseline signal. Functional runs will last 9min 20s, comprising a total of 40 trials (20 experimental and 20 control). 4 such runs will be conducted.

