Specific Aim I will test the hypothesis that spatial cognitive training of blind veterans on a spatial imagery task leads to improvements in **(a)** performance on the trained spatial imagery task and **(b)** real-world navigational ability, relative to a control intervention. If the hypothesis is supported, this would be a simple method of spatial cognitive training with real-world benefits that could eventually be administered via telemedicine. **Specific Aim II** will use functional magnetic resonance imaging (fMRI) to assess the neural changes associated with spatial cognitive training. The hypothesis is that those in the spatial cognitive training group will show enhanced activation in brain regions mediating spatial processing, such as the hippocampus and parietal cortex, as well as more differentiated neural representations of imagined paths. The benefit of pinpointing the neural loci of change is the identification of potential targets for application of converging rehabilitation approaches, e.g. transcranial magnetic or electrical stimulation over parietal regions; enhancing hippocampal neurogenesis through aerobic exercise. If the present proposal is successful, subsequent research will be needed to determine how best to incorporate such training into programs that complement current O&M training.

ANALYSES

In **Specific Aim I**, each behavioral measure will be subjected to a repeated-measures ANOVA with a between-subjects factor of group (experimental, control) and a within-subjects factor of session (pre-training, post-training); the null hypothesis will be rejected in case the interaction is significant at $\alpha=0.05$. If the interaction is non-significant, the Bayes factor will be calculated to ascertain whether this (less likely) supports the null hypothesis or (more likely) reflects insufficient power (Dienes, 2014); in the latter case, the data can be used to estimate the sample size for a subsequent study. In **Specific Aim II**, the imaging measures acquired (except

for DTI) will be subjected to similar two-factor ANOVAs as in Aim I, and statistical interpretations will follow similar lines.

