We predict that spatial cognitive training, but not the control intervention, will lead to improvements in performance on the spatial imagery task, its analog in the MSL, and the various functional neuroimaging measures. There may be transfer of spatial learning to the spatial memory task, but we do not expect transfer to the verbal memory and working memory measures, indicating the spatial specificity of training. We hypothesize that spatial cognitive training, but not training on the control intervention, will lead to increases in activation in cortex along the IPS and in the FEFs as well as in the hippocampus, increased strength of connectivity between these regions in the task and resting states, and also to more differentiated representations between different paths (i.e. their representations will show higher dissimilarity). The behavioral and neuroimaging measures obtained at baseline, including DTI measures of structural connectivity between the activated brain regions, will be tested as regressors to establish whether they predict changes in the repeated measures. This will be useful to examine the impact of individual differences in pre-training spatial and verbal abilities on the effects of training, and in the design of further studies aimed at targeting interventions tuned to individual performance in specific domains.

TIMELINE

First 2 months: Set up tasks and initiate recruitment

Next 20 months: Test and train 2 subjects per month, one in each group

Last 2 months: Analyze data and prepare publications

FUTURE DIRECTIONS

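### No rule says whether accuracy or response time decides Aim I(a), and the imaging tests appear to use the same unadjusted 0.05 with no error control

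*Combined protocol and SAP*

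**What the plan says.** ANALYSES, Specific Aim I: each behavioural measure has its own repeated-measures ANOVA (group by session), and "the null hypothesis will be rejected in case the interaction is significant at" 0.05. A Bayes factor follows only when the interaction is not significant.

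PROCEDURES, Behavioral measures, defines the imagery-task outcome: "Performance (directional accuracy and response time [RT]) on the spatial imagery task will be acquired during fMRI scanning". These are two measures for Aim I(a). For Aim I(b), Real-world task gives one: "performance will be measured as the angular error of pointing".

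ANALYSES, Specific Aim II: the imaging measures other than DTI "will be subjected to similar two-factor ANOVAs as in Aim I, and statistical interpretations will follow similar lines". Imaging measures lists four such types: activation magnitude, representational similarity of paths, task-based effective connectivity and resting-state connectivity.

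The predictions in ANALYSES give a direction, expecting "improvements in performance on the spatial imagery task, its analog in the MSL, and the various functional neuroimaging measures", and name regions: "increases in activation in cortex along the IPS and in the FEFs as well as in the hippocampus". They expect no transfer to the verbal measures.

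The document names no primary measure, combined score, testing order or multiplicity adjustment. For imaging it gives no cluster-level, family-wise or false-discovery correction.

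**The concern.** Accuracy and RT can move apart, for example when participants become slower but more accurate. The rejection rule is written per measure and states no direction, so a split result leaves Aim I(a) undecided. The choice of which measure counts would then be made after the results are known.

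For imaging, the rule seems to be repeated over at least four outcome types and several regions and connections. The Bayes factor step cannot limit false positives, because it applies only to non-significant results. A chance finding could be taken for a neural locus of change, which the document would use to choose targets for stimulation or other converging treatments. The study is a proof of concept, so the likely harm is a misleading basis for the larger study under FUTURE DIRECTIONS.

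**Working it through.** **Inputs.** Alpha is 0.05 per test (ANALYSES). Aim I(a) has two measures and Aim I(b) one (PROCEDURES). There are four non-DTI imaging types. PARTICIPANTS gives 60 participants in two groups and power 0.81 for an effect of 0.9, with no endpoint named. One-to-one allocation is inferred from TIMELINE ("Test and train 2 subjects per month, one in each group"). The correlations between test statistics (0, 0.5, 0.8) are my assumption.

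**The plan's own power figure.** By the normal approximation, power = Φ(0.9 × √(n/2) − 1.96).
- 30 per group: Φ(3.486 − 1.960) = 0.94; the t test gives 0.929.
- 20 per group: Φ(2.846 − 1.960) = 0.812; the t test gives 0.792.

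The stated 0.81 therefore fits 40 participants, which is also the TIMELINE total (20 months × 2), and not 60. PARTICIPANTS and TIMELINE need reconciling, so both cases are shown.

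**Undecided outcomes for Aim I(a).** Assume the effect of 0.9 holds for both measures. P(exactly one significant) = 2 × (power − P(both)), with P(both) from a bivariate normal.

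| Correlation | Power 0.929: both | exactly one | Power 0.81: both | exactly one |
|---|---|---|---|---|
| 0 | 0.863 | 13% | 0.656 | 31% |
| 0.5 | 0.878 | 10% | 0.701 | 22% |
| 0.8 | 0.895 | 7% | 0.741 | 14% |

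For correlation 0 at power 0.81: 2 × (0.81 − 0.81²) = 2 × (0.81 − 0.656) = 0.308.

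**False improvement on Aim I(a).** With two groups and two sessions the interaction is a 1-df test, equivalent to a two-sided t test on change. Each measure therefore carries 0.05/2 = 2.5% in the favourable direction.
- Either measure may count: at most 0.025 + 0.025 = 5%. The value is 1 − 0.975² = 4.9% if independent, 4.5% at correlation 0.5 and 3.9% at 0.8.
- One named measure, or both required: at most 2.5%.

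**Imaging.** Assume one test per non-DTI type, the fewest possible. The chance of at least one false rejection is 1 − 0.95⁴ = 18.5% if independent, 15.6% at correlation 0.5 and 11.4% at 0.8. In the predicted direction only, it is 9.6%, 7.8% and 5.7%. One Benjamini-Hochberg procedure at 5% over the four tests, with every null true, gives 5.0%, 4.6% and 3.8% by simulation.

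**The case against.** **The inflation on (a) is conditional and small.** This stands. A reader might infer that the plan doubles the false-improvement rate for (a). It does so only under an either-may-count rule that the document never states. The 2.5% benchmark is derived from the two-sided test, and even the worst case does not exceed the plan's nominal 0.05. Aim I is also worded as (a) and (b) together. If neither effect exists and the tests are independent, a false full claim has probability of about 0.049 × 0.025 = 0.12%. The verbal measures add no route to false success, because no transfer to them is predicted.

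**The study is a proof of concept.** This also stands: the stated purposes are feasibility, effect-size data and mechanism. It lowers the stakes, but the plan still sets a reject-or-not rule and makes further steps depend on success, so success has to be defined.

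**No imaging threshold is written out.** True. Applying 0.05 is the natural reading of the reference back to Aim I, but it is a reading, and four tests is an assumed count.

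**Resting-state seeds.** Taking "patterns using the activated regions as seeds" might be thought to bias the resting-state tests. The document does not support that inference. The activation contrast appears to be the task contrast (imagery against odd/even trials). Nothing says that seeds are chosen on the group-by-session interaction being tested.

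**Conclusion.** The point holds as a gap in the decision rule. Aim I(a) has two measures and no deciding one. With 30 per group the two would disagree on significance in 7% to 13% of trials, or in 14% to 31% at the stated power. Both ranges assume an effect of 0.9 on each measure, which the document attaches to no endpoint. Inflation of the false-improvement rate on (a) is possible but not established.

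For Aim II the plan states no error control. Under the natural reading of its cross-reference, even four tests carry an 11.4% to 18.5% chance of at least one false rejection over correlations from 0.8 to 0. Further tests would raise it, and the true number is not stated.

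This should be corrected, but it does not undermine the design.

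**What to change.** Amend ANALYSES before data are seen.

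1. **Aim I.** Name one deciding measure for (a) and pointing error for (b). Directional accuracy is suggested for (a), because the real-world analog is also scored on direction; the document does not rule out RT. First reconcile how direction is recorded: Spatial imagery task describes a joystick response, Imaging design a keypress.
2. **Claims.** Claim the full Aim I hypothesis only if both interactions are significant at two-sided 0.05 in the favourable direction. No alpha split is needed. If only one is significant, report that part alone and state that the chance of at least one false favourable part is up to 5% (0.025 + 0.025).
3. **Secondary measures.** Report RT, the Corsi test and the verbal measures as estimates with 95% confidence intervals.
4. **Aim II.** List the regional and connectivity tests on the IPS, FEF and hippocampus and the path-dissimilarity test. Apply one Benjamini-Hochberg procedure at 5% across all four non-DTI types. Use cluster-level family-wise correction for any whole-brain map.

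**Cost.** This is wording only, with no new data.
- RT alone can no longer support (a).
- The chance that (a) and (b) both succeed, assuming 0.9 on each, is 0.86 to 0.90 with 30 per group, or 0.66 to 0.74 at power 0.81. The wording of Aim I already implies this.
- An isolated imaging result among four tests needs p ≤ 0.05/4 = 0.0125. At an assumed effect of 0.9, its power (t test) falls from 0.93 to 0.81 with 30 per group, or from 0.79 to 0.59 with 20 per group.

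### Spatial specificity is to be read from absent verbal transfer, but no planned analysis compares the spatial effect with the verbal effect

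*Combined protocol and SAP*

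**What the plan says.** All points are in the combined protocol and SAP.

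- **Test (ANALYSES, Specific Aim I).** "each behavioral measure will be subjected to a repeated-measures ANOVA with a between-subjects factor of group (experimental, control"), crossed with time of testing (before or after training) as the repeated factor. The decision rule for each measure is that "the null hypothesis will be rejected in case the interaction is significant at" the 0.05 level. There is no domain or measure factor.
- **Non-significant results (same paragraph).** "If the interaction is non-significant, the Bayes factor will be calculated to ascertain whether this (less likely) supports the null hypothesis"; the alternative offered is low power, which the plan calls the likelier explanation. It names no prior and no threshold.
- **Interpretation (ANALYSES, predictions).** For the Corsi test: "There may be transfer of spatial learning to the spatial memory task". For the verbal tests: "we do not expect transfer to the verbal memory and working memory measures, indicating the spatial specificity of training".
- **Measures (Behavioral measures).** Spatial memory is a haptic Corsi block test. The verbal side is "the verbal memory tests of immediate and delayed memory from the RBANS" plus forward and backward digit span, taken here as four scores.

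No contrast of spatial against verbal effects is planned anywhere. Under Preliminary Studies, the group says that its earlier imaging work used a task-by-session interaction to isolate training-specific effects. The behavioral analysis has no counterpart to this.

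**The concern.** Specificity is a statement about a difference between two effects. A significant result on one measure beside a non-significant result on another does not establish such a difference. The verbal test may simply have missed a gain of similar size. The Bayes factor asks whether one verbal effect is zero, which is useful, but it never sets that effect against the spatial one. The predictions paragraph does not tie the specificity conclusion to it either.

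At stake is a secondary interpretation: whether gains are described as spatial or as more general. It matters because the project is meant to supply effect-size data and support an application for a larger study, so an untested description could be carried into that design.

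**Working it through.** **The plan's own figure.** PARTICIPANTS gives power 0.81 for an effect of 0.9 with 60 participants. With two-sided alpha 0.05 and a standardised difference, power at 30 per arm is 0.929 (t) or 0.936 (normal), so 0.81 is not reproduced. At 20 per arm it is 0.792 (t) or 0.812 (normal). TIMELINE implies 20 per arm (2 per month × 20 months = 40). That mismatch is a separate matter. Here 30 per arm is the main case and 20 per arm the check.

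**Assumptions not in the documents.** Equal true standardised effects on one spatial and four verbal change scores; correlation r between change scores of 0 to 0.5; two-sided tests. A t-test on change scores is equivalent to the group-by-session F test.

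**Step 1: single-test power, t with noncentrality d√(n/2).**
- d=0.5: 0.478 at 30 per arm, 0.338 at 20 per arm.
- d=0.4: 0.332 at 30 per arm, so a real verbal gain of that size is missed with probability 1 − 0.332 = 0.668. At 20 per arm it is missed in 77%.

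**Step 2: the misleading pattern when r=0 and d=0.5.**
- One given verbal test non-significant: 0.478 × 0.522 = 0.250 (30 per arm); 0.338 × 0.662 = 0.224 (20 per arm).
- All four non-significant: 0.478 × 0.522⁴ = 0.478 × 0.0743 = 0.036 (30 per arm); 0.338 × 0.662⁴ = 0.338 × 0.192 = 0.065 (20 per arm).

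**Step 3: simulation with correlated scores, d=0.5, 30 per arm.**

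| Spatial test significant and… | r=0 | r=0.3 | r=0.5 |
|---|---|---|---|
| one given verbal test non-significant | 25% | 20% | 17% |
| all four verbal tests non-significant | 3.6% | 3.9% | 3.5% |
| one verbal Bayes factor supports the null* | 6% | 3% | 2% |

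*Assumed JZS prior, scale 0.707, BF01>3.

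If any one of the four counted, the rate would be 33% to 45%. If all four Bayes factors had to support the null, it would be at most about 0.03%. The all-four rate without the Bayes factor is about 4% to 8% at d=0.3 and at most about 0.2% at d=0.9. A direct contrast rejects in 5% of such trials, about 2.5% in the spatial direction.

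**Step 4: what the Bayes factor can deliver.** With a true verbal effect of exactly zero, BF01>3 is reached in only 55% of trials at 30 per arm and 34% at 20 per arm. Under that bar the plan would often have no verdict on the verbal measures.

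**Step 5: an example at 30 per arm.** Observed d=0.70 (spatial) gives t = 0.70 × √15 = 2.71, p=0.009. Observed d=0.50 (verbal) gives t=1.94, p=0.058. This fits the predicted pattern. The difference has standardised size 0.20/√(2(1−r)): 0.141 at r=0 (t=0.55, p=0.59) and 0.20 at r=0.5 (t=0.77, p=0.44). Nothing here shows that the effects differ.

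**Step 6: power of a direct contrast against the four-score average.** The variance of spatial minus average verbal, in units of one change-score variance, is 1 + (1+3r)/4 − 2r = 1.25(1−r). For d=0.5 against 0 at 30 per arm, the standardised effect 0.5/√(1.25(1−r)) is 0.447, 0.535 and 0.632 at r=0, 0.3 and 0.5, giving power 0.40, 0.53 and 0.67. The single spatial test has 0.48. The contrast gains power once 1.25(1−r) < 1, that is r > 0.2. Telling a large from a moderate effect is harder: for 0.9 against 0.5 with one verbal score, power is 0.19 to 0.33.

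**The case against.** The strongest reply has four parts.

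- **It is a prediction, not a rule.** The sentence comes in a paragraph of expected results. A reader might infer that a verbal p-value above 0.05 will itself be taken as proof of specificity. The documents do not say that, and every non-significant interaction goes to a Bayes factor. This stands. What remains is that the plan names the inference and supplies no test for it.
- **The 17% to 25% range is not the risk of the stated inference.** A reader might take it as the false-claim rate. It applies to one chosen verbal test and ignores the Bayes factor, whereas the sentence covers the verbal measures together. The matching figure is about 4% at d=0.5, not far above the 2.5% of a direct contrast. This also stands, although the plan does not say how many verbal measures must be null or what Bayes factor suffices.
- **Non-specific effects are handled elsewhere.** A reader might infer that the verbal tests are the safeguard against attention or expectancy. The documents link them only to spatial specificity. The randomised active control, delivered with a similar setup, and the group-by-session interaction address non-specific effects.
- **Nothing primary depends on it.** Specificity is in neither Specific Aim, and the study is a proof of concept. This limits the weight of the point but does not supply the missing comparison.

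A fair objection to the remedy is that resting it on Corsi alone would be narrow, since the plan says only that transfer there may occur.

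**Conclusion.** The concern holds as a gap in a secondary interpretation. The plan anticipates a specificity conclusion, but its analyses test each effect against zero and never against each other. The Bayes factor lowers the risk of a false claim without answering that question, and the plan's own view that non-significance more likely reflects low power sits poorly with reading it as evidence of specificity.

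The size is small to moderate and depends on a rule that the plan leaves open: about 4% if all four verbal tests must be non-significant, 17% to 25% for one given test, and about 6% or less for one test if the Bayes factor must support the null. The first two assume equal true effects of d=0.5, 30 per arm and r of 0 to 0.5; the last also rests on an assumed prior and threshold. Aims I(a) and I(b) are not affected.

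**What to change.** Prespecify one secondary analysis: a group-by-session-by-domain contrast on standardised change scores, with untrained spatial memory (Corsi) against the average of the RBANS verbal and digit-span scores. State the standardising SD in advance, and sign every score so that higher is better. Run the same contrast for the real-world pointing task as supportive evidence. Leave the trained imagery task out of this claim, because it mixes domain with practice.

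Report the 95% CI for the difference between domain effects and 95% CIs for the verbal effects. Describe training as spatially specific only where the CI for the difference excludes zero in the spatial direction; otherwise report specificity as unresolved. If the Bayes factor is kept for the verbal measures, state its prior and threshold.

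The cost is one extra analysis on data already to be collected, with no added visits or participants. The contrast may have less or more power than a single-domain test depending on the correlation between measures, so specificity may well stay unresolved in a study of this size.
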